## PROTOCOL SYNOPSIS

Sponsor: Covidien - Neurovascular [name] [name] Telephone:	Protocol Number: NV-PED-07
	Product: Pipeline™ Embolization Device 
	Regulatory Class: III
	Development Phase: IV
Title: Prospective study on embolization of intracranial aneurysms with Pipeline™ Embolization Device (PREMIER)	
Study Design: The study is a global, prospective, single-arm, multi-center clinical study evaluating outcomes in subjects with intracranial aneurysms measuring ≤ 12 mm who are treated with Pipeline™ device.	
Objective: To assess the safety and effectiveness of the Pipeline™ device in the treatment of unruptured, wide-necked, intracranial aneurysms measuring ≤ 12 mm, located in the internal carotid artery (up to the terminus) or the vertebral artery segment up to and including the posterior inferior cerebellar artery.	
Background: Intracranial aneurysms (IAs) measuring ≤ 12 mm in size comprise approximately 80% of all intracranial aneurysms.  IAs can rupture suddenly and without warning, leading to cerebral bleeding or subarachnoid hemorrhage (SAH). SAH is a devastating complication with a case-fatality rate of 45%.  The average size of ruptured IAs is approximately 6.6 to 6.8 mm.  In order to prevent aneurysmal rupture, small and medium wide-necked IAs are commonly treated endovascularly with stent-assisted coiling. Although initial occlusion rates are good, the primary limitation of stent-assisted coiling is the inability to provide sustained long-term aneurysm occlusion. Aneurysm recurrence rates of up to 16% have been reported in the literature after stent-assisted coil treatment of small and medium IAs.  The presence of major aneurysm recurrence requires retreatment up to 10% for small and medium IAs.  indicating current treatment outcomes are sub-optimal. Therefore, an alternative approach for obtaining sustained aneurysm occlusion is needed for small and medium wide-necked IAs.  Recently, flow-diverting devices represent a paradigm shift in the endovascular treatment philosophy for IAs. At present, the only FDA-approved flow diverter is the Pipeline™ device, which is indicated for the endovascular treatment of adults (22 years of age or older) with large or giant wide-necked IAs in the ICA from the petrous to the superior hypophyseal segments. Clinical trial data from the PUFs study have shown that 87.4% of the target IAs were completely occluded at one year. There were no cases of aneurysm recurrence. The rate of ipsilateral major stroke or neurologic death at 1-year follow-up was 5.6%. In addition, published data on the Pipeline™ device used to treat complex large/giant aneurysms show rates of 68-94.4% complete occlusion that remains persistent 2-3 years after the index procedure and 0-13.9% associated morbidity and 0%-6.4% mortality.  These rates are similar to or better than those for conventional IA treatments of surgery or coiling. 	

 And future devices upon approval by FDA

## PROTOCOL SYNOPSIS

Sponsor: Covidien - Neurovascular [name] [name] Telephone:	Protocol Number: NV-PED-07
	Product: Pipeline™ Embolization Device 
	Regulatory Class: III
	Development Phase: IV

Currently, treatment with the Pipeline™ device is indicated for IAs in the ICA from the petrous to the superior hypophyseal segments and the present study aims to include IAs in the ICA up to the terminus. Data from 277 patients with IAs ≤ 12 mm located in the ICA up to the terminus were collected in the IntrePED retrospective study, which demonstrate neurological morbidity and mortality rates of 2.9% and 1.1%, respectively. These rates demonstrate that the Pipeline™ device can serve as a potentially safe treatment option for IAs of the ICA (up to the terminus). The treatment of IAs in the posterior circulation is typically associated with a higher rate of complications. However when limited to only the vertebral and posterior inferior cerebellar arteries, published literature indicates that the morbidity and mortality rates are similar to the rates reported for stent-assisted coil treatment of small-wide-necked IAs. Studies evaluating the treatment of aneurysms located in the VA or PICA demonstrate morbidity rates ranging 0%-13% and mortality rates ranging 0%-7%. These rates are comparable to the stent-assisted coiling morbidity rates of 3.9%-9.2% and mortality rates of 0%-6.8%. Within this current study, the safety and effectiveness of the Pipeline™ device for the treatment of unruptured wide-necked IAs measuring ≤ 12 mm in the vertebral artery segment up to and including the PICA will be investigated.

Number of Subjects: Up to 200 subjects enrolled to ensure 141 treated subjects	Number of Study Centers: Up to 28 study centers
--	---

### Duration of Study Participation:

- Enrollment Duration: Approximately 18 months
- Follow-up: 3 years
- Total Study Duration: Approximately 54 months

### Primary Endpoints:

- Safety: Occurrence of major stroke in the territory supplied by the treated artery or neurological death at 1 year post-procedure
- Effectiveness: Complete aneurysm occlusion (defined by scale of Roy) without significant parent artery stenosis (≤ 50%) at 1 year post-procedure

### Secondary Endpoints:

- Safety:
  - Occurrence of major stroke in the territory supplied by the treated artery or neurological death at 30 days post-procedure due to procedural complications
  - Delayed intracerebral hemorrhage >30 days post-procedure
- Effectiveness: Device deployment success rate at the target site

## PROTOCOL SYNOPSIS

Sponsor: Covidien - Neurovascular [name] [name] Telephone:	Protocol Number: NV-PED-07 Product: Pipeline™ Embolization Device  Regulatory Class: III Development Phase: IV
--	---

### Additional Data:

- Device-related neurologic adverse event rate by 1 year post-procedure
- Modified Rankin Scale (mRS) score at 1 year
- Aneurysm occlusion at 3 years post-procedure
- Recurrence and retreatment rates at 1, 2 and 3 years post-procedure
- Procedure time
- Radiation exposure (dosage and time)
- Number of Pipeline™ devices utilized

### Inclusion Criteria:

1. Subject has provided written informed consent using the IRB/EC-approved consent form and agrees to comply with protocol requirements.
2. Age 22-80 years.
3. Subject has a target intracranial aneurysm (IA) located in the:
  - a) Internal carotid artery (up to the carotid terminus) OR
  - b) Vertebral artery segment up to and including the posterior inferior cerebellar artery
4. Subject has a target IA that is  $\leq 12$  mm.
5. Subject has a target IA that has a parent vessel with diameter 1.5–5.0 mm distal/proximal to the target IA.
6. Subject has a target IA with an aneurysm neck  $\geq 4$  mm or a dome to neck ratio  $\leq 1.5$ .
7. Subject has a pre-procedure PRU value between 60–200.

## PROTOCOL SYNOPSIS

Sponsor: Covidien - Neurovascular [name] [name] Telephone:	Protocol Number: NV-PED-07
	Product: Pipeline™ Embolization Device
	Regulatory Class: III
	Development Phase: IV

### Exclusion Criteria:

1. Subject has received an intracranial implant (e.g. coils) in the area of the target IA within the past 12 weeks.
2. Subarachnoid hemorrhage in the past 30 days.
3. Subject with anatomy not appropriate for endovascular treatment due to severe intracranial vessel tortuosity or stenosis determined from baseline or pre-procedure imaging, or a history of intracranial vasospasm not responsive to medical therapy.
4. Major surgery in the last 30 days.
5. History of irreversible bleeding disorder and/or subject presents with signs of active bleeding.
6. Any known contraindication to treatment with the Pipeline™ device, including:
  - a. Stent is in place in the parent artery at the target IA location
  - b. Contraindication to dual antiplatelet therapy
  - c. Relative contraindication to angiography (e.g., serum creatinine >2.5 mg/dL, allergy to contrast that cannot be medically controlled).
  - d. Known severe allergy to platinum or cobalt/chromium alloys.
  - e. Evidence of active infection at the time of treatment (e.g., fever with temperature >38°C and/or WBC >1.5 10^9/L).
7. The Investigator determines that the health of the subject or the validity of the study outcomes (e.g., high risk of neurologic events, worsening of clinical condition in the last 30 days) may be compromised by the subject's enrollment.
8. Pregnant or breast-feeding women or women who wish to become pregnant during the length of study participation.
9. Participating in another clinical trial during the follow-up period that could confound the treatment or outcomes of this investigation.

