## PROTOCOL SYNOPSIS

**Sponsor: Covidien - Neurovascular**  
**[name]**  
**[name]**  
**Telephone:**

**Protocol Number: NV-PED-07**

**Product: Pipeline™ Embolization Device**

**Regulatory Class: III**

**Development Phase: IV**

### Treatment/Follow-up:

Eligible subjects will be treated with the Pipeline™ device.

The study will consist of the following study visits:

- Baseline
- Procedure
- Discharge exam
- Follow-up at 30-day, 180-day, 1-year, 2-year, and 3-year post-procedure

A schedule of assessments to be performed at each study visit is listed in the table below.

Visit and Assessment Schedule									
Visits		Screening and Baseline	Device placement		Follow-up				
Assessments	Time (Windows)		Procedure	Discharge exam	30-day	180-day	1-year	2-year	3-year
	Pre-procedure (-60 days)		Day 0	Day 0-7	Day 30 (± 7 days)	Day 180 (± 30 days)	Day 365 (± 42 days)	Day 730 (± 42 days)	Day 1095 (± 42 days)
Assess Inclusion / Exclusion		◆							--
Demographics and Medical History		◆							
Blood Labs	◆ 	◆ 	○ 						
Medications	◆	◆	◆	◆	◆	◆	◆	◆	◆
Modified Rankin Scale score	◆		◆	◆	◆	◆	◆	◆	
Imaging 	◆ (180 days)	◆ 			○ 	◆	◆ 	◆ 	◆ 
NIH Stroke Scale	◆	◆	◆	◆	◆	◆	◆	◆	◆
Pipeline™ Placement			◆						
Assess Adverse Events	◆	◆	◆	◆	◆	◆	◆	◆	◆

1 Includes CBC, HCT, platelet count, platelet function testing as per standard patient care, serum creatinine, and pregnancy test, if applicable

2 Includes platelet count and platelet function testing

3 If platelet function testing is performed as standard patient care the results should be recorded.

4 Angiograms in the anteroposterior, lateral and working positions for analysis by a core laboratory.

5 Includes a pre-treatment and post-treatment angiogram

6 If an angiogram is performed as standard patient care it should be sent to the core laboratory for analysis.

7 If aneurysm is completely occluded at 1 year, angiography is optional at subsequent follow-up visits. Otherwise if aneurysm is not occluded at 1 year, angiography must be performed thereafter until the aneurysm is completely occluded or the subject has completed the study.

Any angiograms performed at other time points should be sent to the core laboratory for analysis.

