### 4.1 Number of Sites and Subjects

Up to 200 subjects will be enrolled at up to 28 sites worldwide over a period of approximately 18 months to ensure the study has an adequate number of treated subjects; up to 141 (see **Section 9.2**). The enrollment number takes into account an approximate 30% screen failure rate observed in the initial roll-out of the PREMIER study. Each participating investigational site will be allowed to enroll a maximum of 25 subjects who meet all study eligibility criteria (see **Section 4.3**) and are treated with the Pipeline™ device.

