#### **4.3.2 Exclusion Criteria**

The subject must not meet any of the following general exclusion criteria:

[figure not shown]
1. Subject has received an intracranial implant (e.g. coils) in the area of the target IA within the past 12 weeks.
2. Subarachnoid hemorrhage in the past 30 days.
3. Subject with anatomy not appropriate for endovascular treatment due to severe intracranial vessel tortuosity or stenosis determined from baseline or pre-procedure imaging, or a history of intracranial vasospasm not responsive to medical therapy.
4. Major surgery in the last 30 days.
5. History of irreversible bleeding disorder and/or subject presents with signs of active bleeding.
6. Any known contraindication to treatment with the Pipeline™ device, including:
  - a. Stent is in place in the parent artery at the target IA location
  - b. Contraindication to dual antiplatelet therapy
  - c. Relative contraindication to angiography (e.g., serum creatinine  $>2.5$  mg/dL, allergy to contrast that cannot be medically controlled).
  - d. Known severe allergy to platinum or cobalt/chromium alloys.
  - e. Evidence of active infection at the time of treatment (e.g., fever with temperature  $>38^{\circ}\text{C}$  and/or WBC  $>1.5 \cdot 10^9/\text{L}$ ).
7. The Investigator determines that the health of the subject or the validity of the study outcomes (e.g., high risk of neurologic events, worsening of clinical condition in the last 30 days) may be compromised by the subject's enrollment.
8. Pregnant or breast-feeding women or women who wish to become pregnant during the length of study participation.
9. Participating in another clinical trial during the follow-up period that could confound the treatment or outcomes of this investigation.

Before any subject is treated in the study, the baseline angiogram will be reviewed by a Pipeline™ device expert to ensure that the target IA is amenable to treatment with the Pipeline™ device.

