### **5.3 Screening and Baseline Evaluations**

Each subject will undergo a neurologic examination and assessment using the mRS and NIHSS, blood draw for hematocrit, platelet count, platelet function testing as per standard patient care (e.g. using VerifyNow (Accumetrics)), serum creatinine, and a pregnancy test (if applicable) within 60 days from the planned procedure. In female subjects, pregnancy may be ruled out by urine or blood pregnancy test, or medical history (menopause or surgical sterility). Each subject's relevant medical history and pre-existing conditions will be assessed and documented for all enrolled subjects. Current medication use within the last 30 days will be assessed and documented at baseline.

Subject eligibility assessment is to be performed based on data available to the investigator at the time of screening. This initial screening phase may include review of existing subject information (previously performed angiography, radiographs, laboratory studies, medical history, physical examination, etc.) and referral to the treating physician. Subjects must comply with all inclusion and exclusion criteria. Waivers will not be granted by the sponsor regarding subject inclusion/exclusion criteria.

If the subject meets the dimensional criteria outlined in the inclusion criteria, they should be included on the study screening log. The reason of non-eligibility for all subjects who are deemed ineligible by the Investigator should also be recorded on the study screening log. The screening log serves as a method for Covidien to ensure that there is no selection bias in the trial.

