## 5.8 Schedule of Assessments

An overview of the assessments to be performed at each follow-up interval along with the required timing is provided in **Table 5**. Visits occurring outside of the specified date range will be considered protocol deviations.

Visits		Screening and Baseline	Device placement		Follow-up					
Assessments	Time (Windows)	Pre-procedure (-60days)	Procedure	Discharge exam	30-day	180-day	1-year	2-year	3-year	Unscheduled
Assess Inclusion / Exclusion		◆								
Demographics and Medical History		◆								
Blood Labs		◆ 	◆ 	○ 						
Medications		◆	◆	◆	◆	◆	◆	◆	◆	◆
Modified Rankin Scale score		◆		◆	◆	◆	◆	◆	◆	
Imaging 	(180 days)	◆ 			○ 	◆	◆ 	◆ 	◆ 	
NIH Stroke Scale		◆	◆	◆	◆	◆	◆	◆	◆	◆
Pipeline™ Placement			◆							
Assess Adverse Events		◆	◆	◆	◆	◆	◆	◆	◆	

1 Includes CBC, HCT, platelet count, platelet function testing as per standard patient care, serum creatinine, and pregnancy test, if applicable

2 Includes platelet count and platelet function testing

3 If platelet function testing is performed as standard patient care the results should be recorded.

4 Includes angiograms in the anteroposterior, lateral and working positions for analysis by a core laboratory.

5 Includes a pre-treatment and post-treatment angiogram

6 If an angiogram is performed as standard patient care it should be sent to the core laboratory for analysis.

7 If aneurysm is completely occluded at 1 year, angiography is optional at subsequent follow-up visits. Otherwise if aneurysm is not occluded at 1 year, angiography must be performed thereafter until the aneurysm is completely occluded or the subject has completed the study.

Any angiograms performed at other time points should be sent to the core laboratory for analysis.

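### Exclusion 6e gives a white cell count above 1.5 × 10⁹/L as an example of active infection, a level that nearly every uninfected adult exceeds

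*Combined protocol and SAP*

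**What the plan says.** Item 6e of the exclusion criteria appears twice, in the synopsis and in Section 4.3.2. The synopsis wording is "Evidence of active infection at the time of treatment (e.g., fever with temperature >38°C and/or WBC >1.5 10 9 /L". Section 4.3.2 opens the item in the same way ("Evidence of active infection at the time of treatment") and prints the same value, exponent and unit. No other section gives a white-count threshold or a reference range.

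Three further statements determine how 6e operates:

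- Section 4.3.2 introduces the list with "The subject must not meet any of the following general exclusion criteria", so one exclusion is enough.
- Section 5.3 adds: "Waivers will not be granted by the sponsor regarding subject inclusion/exclusion criteria".
- The assessment schedule (synopsis, and Table 5 in Section 5.8) describes the screening bloods as "Includes CBC, HCT, platelet count, platelet function testing as per standard patient care, serum creatinine, and pregnancy test, if applicable", and the procedure-day bloods as "Includes platelet count and platelet function testing". The screening window runs to 60 days before the procedure.

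On how many candidates are expected to pass, the synopsis states "Up to 200 subjects enrolled to ensure 141 treated subjects" and Section 4.1 explains: "The enrollment number takes into account an approximate 30% screen failure rate observed in the initial roll-out of the PREMIER study".

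**The concern.** A count used as evidence of infection should be one that uninfected people seldom reach. The printed 1.5 × 10⁹/L is 1,500 cells per microlitre, which is low for a healthy adult. Because *and/or* joins it to fever, the count by itself is enough to meet the example.

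Two things are at stake. First, 6e protects subjects before a permanent intracranial implant. If one of its two worked examples is unusable, each site has to decide for itself what counts as a raised white count, and the decisions cannot be audited against a common rule. Second, on a strict reading nearly every treated subject meets an exclusion for which no waiver is available. That leaves a body of technical eligibility failures to be explained at monitoring and when the per-protocol set is drawn up.

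A related loose end is timing. The criterion is judged at treatment, but the schedule names a blood count only at screening.

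**Working it through.** **Inputs from the documents.** Threshold 1.5 × 10⁹/L (synopsis and Section 4.3.2, item 6e); 200 enrolled and 141 treated (synopsis and Section 4.1); screen failure about 30% (Section 4.1).

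**Assumed input.** The adult 95% reference range for white count. The documents give none, so it is varied from 3.0–10.0 to 4.5–11.0 × 10⁹/L, with both a normal and a lognormal shape.

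**Step 1. Reproduce the plan's own figure.** 141 / (1 − 0.30) = 201.4, or 202 rounded up, against 200 stated. In reverse, 1 − 141/200 = 29.5%. The enrolment figure agrees with a loss of about 30%.

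**Step 2. Compare the threshold with the lower limit of normal.** 3.0/1.5 = 2.0 and 4.5/1.5 = 3.0. The assumed lower limit is 2 to 3 times the printed figure.

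**Step 3. Find the share of uninfected adults above the threshold.** For a range (L, U) and a normal shape, mean = (L + U)/2, SD = (U − L)/(2 × 1.96), and the share is 1 − Φ((1.5 − mean)/SD). For 3.0–10.0 the mean is 6.5, the SD is 7.0/3.92 = 1.786, z = (1.5 − 6.5)/1.786 = −2.80, and the share is 99.74%. The lognormal version uses the same formula on the log scale.

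| Assumed range (× 10⁹/L) | Share above 1.5, normal | Share above 1.5, lognormal | Expected to pass out of 200, normal |
|---|---|---|---|
| 3.0–10.0 | 99.74% | 99.9988% | 0.51 |
| 3.5–10.5 | 99.90% | >99.99% | 0.21 |
| 4.0–11.0 | 99.96% | >99.99% | 0.08 |
| 4.5–11.0 | 99.99% | >99.99% | 0.02 |

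**Step 4. Set this against the plan.** Taken literally, 6e would let through about 0.5 or fewer of 200 uninfected candidates, where the plan needs 141. Equivalently, at least 141 × 0.9974 = 140.6 of 141 treated subjects would meet the white-count example. Literal application implies close to 100% exclusion, while Section 4.1 reports about 30%. The two cannot both describe what sites do.

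**Step 5. Set the timing side by side.** Item 6e refers to the time of treatment. Footnote 1 of the schedule puts a CBC at screening. The blood tests listed in the text of Section 5.3 do not mention a CBC or white count. Footnote 2, for the procedure day, names platelet count and platelet function testing. Section 5.3 also bases eligibility on what the investigator knows at screening. These places do not say which white count 6e refers to.

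**The case against.** The strongest reply is that the operative criterion is evidence of active infection, and that the figures in brackets only illustrate it. This stands in part. The fever example still discriminates, and an investigator can judge infection on other grounds. A reader might infer that 6e cannot detect infection at all, but the wording does not support that. What fails is the white-count example, and with it the combined rule if it is applied literally.

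A reader might also infer that the trial cannot recruit. Section 5.2 places enrolment at consent, so an exclusion bars treatment and not enrolment. The roll-out rate of about 30% also shows that near-total exclusion is not happening. That rate is the only evidence in the documents on the practical effect, and it points to sites not using the printed number.

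A third tempting inference is that the per-protocol set would be empty. Section 9.3 does not define a major deviation, so nothing shows that meeting a misprinted example would count as one. Neither primary analysis uses that set: Section 9.4 names the ITT population and the Full Analysis Set, and Section 9.5 names the Full Analysis Set.

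On timing, footnote 2 says what the procedure-day bloods include, not that they are limited to it. A white count on the day is therefore unnamed, but not ruled out.

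The reference range is an outside assumption. The conclusion is the same across the whole range tried, so little depends on it. A misrendered character in one copy is unlikely, since the synopsis and Section 4.3.2 agree on value, exponent and unit. A slipped decimal or exponent is an easy guess at the cause, but the documents do not show what figure was intended.

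**Conclusion.** The concern holds for the white-count example in 6e, which is **wrong as written** in both places. More than 99.7% of uninfected adults would exceed the printed figure, on the assumption that the adult lower limit of normal lies between 3.0 and 4.5 × 10⁹/L and that white counts are roughly normal or lognormal. With no waivers allowed, nearly every treated subject technically meets an exclusion.

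The consequence is practical and bounded: a pre-implant safety criterion whose laboratory part is left to each site, and treated subjects who are ineligible on paper. No threshold for the primary endpoints, alpha level, sample size or primary analysis depends on it. It still warrants correction, because it is an operative eligibility figure and not background text.

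**What to change.** The sponsor should verify the value, exponent and unit of the white-count figure in item 6e and correct it in both the synopsis and Section 4.3.2. In the same amendment, the reference in 6e to the time of treatment should be reconciled with Section 5.3 and with both copies of the assessment schedule, so that it is clear which white count the criterion refers to. No replacement threshold or timing rule is proposed here; both are for the sponsor to settle.

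The cost is one figure corrected in two places and a short clarification of the schedule text. Correcting the figure adds no visit and no subject. Whether the timing clarification requires any extra laboratory reading depends on how the sponsor resolves it.
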